# 9.16 End of trial

The end of the trial is defined as the date of the collection of the last participant's last data item. Participants will be followed up until death or until the final analysis as described in section 3 Trial design overview, (whichever is sooner). Follow up and trial assessments will continue, including beyond tumour progression.

A separate mechanistic analysis plan will be developed and will be reassessed throughout the duration of the trial given that the mechanistic analysis will not take place until years nine and ten of the grant. The analysis plan will incorporate any developments in the research literature in this field over time.

#### 9.17 Schedule of Assessments

# Table 3 Assessment Schedule for both PBT and photon RT

	Base	eline			Radiotherapy Treatment			Follow-up post-end of radiotherapy									
	Eligibility assessments	Pre- rand	Pre- RT trt	Wk 1	Wk 2	Wk 3	Wk 4	Wk 5	Wk 6	1 month	3 months	6 months	12 months	24 months	36 months	48 months	60 months
Medical history	•																
Clinical Assessment 	•			•	•	•	•	٠	• 	•	•	•	•	•	•	•	•
Neurocognitive function tests 		•								•			•	•	•	•	•
Pregnancy test	• 		• 							• 	• 	• 					
Baseline CTCAE monitoring		•															
MRI scan 		● 	•7								•	•	•	•	•	•	•
CT scan			• 														
Informed consent		•															
HRQoL 		•							• 	•	•	•	•	•	•	•	•
Work & Productivity 		•							• 	•	•	•	•	•	•	•	•
Health Resource Use 		•											•	•	•	•	•
Caregiver Needs Screen 		•							• 	•	•	•	•	•	•	•	•
Endocrine assessment 			•									•	•	•	•	•	•
PBT or photon RT				•	•	•	•	•	•								
PCV Chemotherapy 										6 x 6-w P	veekly cycle CV chemo	es of adjuv therapy	ant				
CTCAE acute & late toxicity monitoring 				•	•	•	•	•	• 	•	•	•	•	•	•	•	•

 Comprised of clinical examination (including CNS examination), documentation of concurrent medications of interest (including review of steroid use, anti-epileptics and hormonal therapies) and assessment of Karnofsky Performance Status to be done within 14 days prior to randomisation.

Participant's height to be done for baseline only, participant's weight to be done at eligibility and prior to Day 1 of each cycle of chemotherapy

 Neurocognitive test. See section 9.10 Neurocognitive function tests

 Participant must have confirmed that they are not pregnant with their doctor/treatment team within 7 days prior to randomisation (see section 4.3.1 Pregnancy Testing)

 Participant must have confirmed that they are not pregnant with their doctor/treatment team within 7 days prior to CT simulation for radiotherapy AND within 7 days prior to the first radiotherapy fraction (4.3.1 Pregnancy Testing)

-  Participant must have confirmed that they are not pregnant with their doctor/treatment team within 7 days prior to each chemotherapy cycle (section 4.3.1 Pregnancy testing)
-  Required to assess response rates and progression-free survival and evaluated based on RANO criteria
-  MRI for radiotherapy planning to be done ideally within 21 days prior to the start of RT, but no more than 28 days of the CT simulation scan
-  CT simulation for RT to be done within 21 days prior to the start of RT
-  Including: EORTC QLQ-C30, EORTC BN20, EQ-5D-5L, Multi-dimensional Fatigue Inventory (MFI), Hospital and Anxiety Depression Scale (HADS)
-  Work & Productivity (WPAI) and Health Resource Use questionnaires will be assessed in participants and primary caregivers. The Health Resource Use will be collected at baseline and at annual follow-up only.
-  Caregiver Needs Screen to be completed by primary caregiver for each participant. Baseline data will also be collected at time of baseline questionnaire completion.
-  To be completed on any day the participant will receive one of their 5 final RT treatments
-  Endocrinopathy: Endocrine function will be assessed using blood tests. Dynamic/static testing will be performed for growth hormone/insulin-like growth factor-1 (GH/IGF-1), follicle-stimulating hormone/luteinizing hormone (FSH/LH)/ testosterone (males) & SHBG (males) /oestradiol (females), cortisol, thyroxine /tri-iodothyronine/ thyroid stimulating hormone (T4/T3/TSH) and prolactin. See section 9.11 Endocrine testing

 Participants may start PCV chemotherapy anywhere between 4 and 8 weeks post-end of RT. For each cycle of chemotherapy, a pre-treatment clinical assessment must be performed within 7 days prior to Day 1 of each cycle. Full blood count, urea and electrolytes, liver function tests, creatinine clearance and bilirubin should be performed within 7 days prior to the first chemotherapy cycle and within 3 days prior to each subsequent chemotherapy cycle  ARs and SARs should be monitored and reported, during trial treatment, up until the end of the trial

 Randomisation must be performed within 28 days of the magnetic resonance imaging (MRI) that leads to the decision that RT is required at that point in time. Outside of 28 days, an updated MRI is required to serve as a contemporaneous baseline scan to assess response to further treatment

# Table 4 Chemotherapy Assessment Sbhedule

	PCV Chemotherapy Treatment								
	Cycle 1 Cycle 2 Cycle 3 Cycle 4 Cycle								
Clinical Assessment 	•	•	•	•	•	•			
Weight	•	•	•	•	•	•			
Blood tests 	•	•	•	•	•	•			
Pregnancy test 	•	•	•	•	•	•			
CTCAE toxicity monitoring 	• • • • • •								

 Pre-treatment clinical assessment must be performed within 7 days prior to day 1 of each cycle, comprising participant's weight, clinical examination including CNS examination, documentation of concurrent medications of interest (including review of steroid use, anti-epileptics and hormonal therapies) and assessment of Karnofsky Performance Status.

 Full blood count, urea and electrolytes, liver functions tests, creatinine clearance and bilirubin should be performed within 7 days prior to the first chemotherapy cycle and within 3 days prior to each subsequent chemotherapy cycle

 Participant must have confirmed that they are not pregnant with their doctor/treatment team within 7 days prior to each chemotherapy cycle (see section 4.3.1 Pregnancy testing)
  ARs and SARs should be monitored and reported throughout trial treatment, including PCV chemotherapy, up until the end of the trial

# 9.18 Trial assessments and data collection

Trial participant data will be collected electronically via the CTRU Remote Data Entry (RDE) database. Participants will be given the choice of completing the HRQoL questionnaires either on paper or electronically, via the electronic patient reported outcome software REDCap. REDCap is the CTRU's current solution for health-related quality of life (HRQoL) data collection and allows trial participants to directly enter data into REDCap, as an alternative to paper-based forms. REDCap has been validated for use in all CTRU trials.

For those wishing to complete the questionnaires electronically, they will be given the option of receiving an email or text message with a link to their questionnaire. Each participant's and caregiver's preferred method of questionnaire administration and completion will be collected during the consent process and applicable contact details (i.e. email address/mobile phone number) collected.

Non-responders will receive reminders by the pre-stated preferred method of communication at the following time points where HRQoL data is collected: during the final week of RT treatment and 1, 3, 6, 12, 24, 36, 48 and 60 months post-end of RT. Reminders will be sent 2 weeks and 4 weeks after the initial link to the questionnaire was sent and where records at CTRU show that it has not been completed. The CTRU will contact sites at intervals throughout the study to ensure that each consenting participant's and caregiver's contact details and status have not changed and that it is still appropriate to send links to the questionnaires.

Participant and caregiver contact details, including email address and mobile phone number (if applicable), will be provided after randomisation to be used to facilitate the administration of HRQoL questionnaires during the trial.

This personal data will only be provided following the provision of informed consent by the participant or caregiver as indicated on the informed consent form and will conform to the 2018 Data Protection Act and General Data Protection Regulation (GDPR).

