# 8 Trial Treatments

# 8.1 Radiotherapy

Radiotherapy will ideally start within 6 weeks of randomisation and must start within 10 weeks of randomisation.

Radiotherapy will also start within 21 days of the CT simulation scan.

An MRI, to assist in radiotherapy planning is required. This is ideally performed within 21 days, but must be performed within 28 days, of the CT simulation scan. The immediate post-operative MRI must NOT be used as a 'planning' MRI as immediate post-operative changes may not have had sufficient time to resolve.

For those randomised to photon RT, during photon RT, the participant will be under the care of the clinician in the local RT centre, who will be responsible for their radiotherapy planning, prescription and delivery. In the lead up to photon RT, during adjuvant chemotherapy and during follow up, the participant will be under the care of the clinician in the local centre.

For those randomised to PBT, during PBT, the participant will be under the care of the clinician in the PBT centre, who will be responsible for their radiotherapy planning, prescription and delivery. In the lead up to PBT, during adjuvant chemotherapy and during follow up, the participant will be under the care of the clinician in the local centre.

RT will be delivered as an outpatient on weekdays over approximately 6 weeks. Throughout this document the relative biological effectiveness (RBE) weighted dose in units of Gray(Gy(RBE)) is used to describe the product of the absorbed dose and the RBE. For PBT, the RBE should be interpreted as 1.1. For photons this should be interpreted as 1 for which Gy(RBE) is equivalent to the absorbed dose in Gy.

The total RT dose will be 54 Gy(RBE) in 30 daily fractions for grade II tumours and 59.4 Gy(RBE) in 33 daily fractions for grade III tumours. Radiotherapy will be delivered on weekdays over approximately 6 weeks (1.8 Gy per daily fraction for all)

Photon RT will be delivered using intensity modulated RT (IMRT) or rotational arc therapy. PBT will be delivered using pencil beam scanning with optimisation, typically performed using single field optimisation (SFO).

Please see the **APPROACH Radiotherapy outlining**, **planning**, **treatment delivery and quality assurance (QA) guidelines** for full details on immobilisation, image acquisition, outlining, planning, treatment delivery, treatment interruptions and quality assurance (QA).

All delineation will be performed at the treating centre.

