## 9.5 Assessments during final week of PBT or photon RT

The following assessments should be completed on any day the participant receives one of their 5 final radiotherapy treatments (i.e. during their final week of treatment). Data collected will include (but will not be limited to):

- As per the weekly assessment above and:
- HRQoL questionnaires (EORTC QLQ-C30, EORTC BN20, EQ-5D-5L, MFI and HADS (completed by participant)),
- WPAI questionnaire and additional health resource use questionnaire (completed by participant and primary caregiver),
- Caregiver Needs Screen questionnaire (completed by primary caregiver).

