#### 9.7 Follow-up assessments

Participants will be seen in the out-patient clinic after completion of PBT or photon RT for follow-up visits (post-end of PBT or photon RT) as follows: 1, 3, 6, 12, 24, 36, 48 and 60 months. Where relevant and possible, follow-up assessments should be performed during the closest chemotherapy pre-treatment assessment and within +/- 4 weeks of the scheduled follow up timepoint. Details of the follow-up assessments required at each of these follow-up time points are provided below.

Follow-up data will be collected at these time points by completing the relevant eCRF. At follow-up visits, data collected will include (but will not be limited to):

- Clinical assessment (clinical examination including CNS examination, documentation of concurrent medications of interest (including review of steroid use, anti-epileptics and hormonal therapies) and assessment of KPS)
- Clinician-recorded toxicities and CTCAE (until end of trial as per assessment schedule)
  - Pre-existing symptoms/side effects related to ODG or its treatment that predate APPROACH trial treatments should be recorded at the baseline assessment – these will not be considered as new toxicities
  - Pre-existing symptoms/side effects related to a non-ODG cause that pre-date APPROACH trial should be recorded at the baseline assessment – these will not be considered as new toxicities
- Neurocognitive function tests (see 9.10 Neurocognitive function tests)
- HRQoL questionnaires (EORTC QLQ-C30 and BN20, EQ-5D-5L, MFI, HADS, completed by participant))
- Endocrine assessment (see 9.11 Endocrine testing; not required at months 1 and 3)
- WPAI questionnaire and an additional health resource use questionnaire (completed by participant and primary caregiver)
- Caregiver Needs Screen questionnaire (completed by primary caregiver)
- MRI (not required at month 1)
- Documentation of clinical or radiological progression

Follow-up visits and assessments will continue until 60 months post-end of radiotherapy or until death, whichever is sooner.

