# 9.12 Participant and caregiver questionnaires

All patients and their primary caregivers will be requested to complete questionnaires at baseline, during the final week of RT treatment and 1, 3, 6, 12, 24, 36, 48 and 60 months post-end of RT. Baseline questionnaires will be completed on paper prior to randomisation in clinic, and patient and caregiver preferred methods for all proceeding questionnaires should be recorded on the F50 Contact Details paper CRF and sent to CTRU via the SFTS.

Both participants and caregivers can choose to either: receive paper questionnaires to be completed in clinic at the appropriate time points; or electronic questionnaires that can be completed online using 'REDCap' which stands for Research Electronic Data Capture (see section 9.18 Trial assessments and data collection for further information).

Where a participant/caregiver has expressed a preference to complete their questionnaires on paper, questionnaires will be completed by the participant/caregiver on attendance at the scheduled outpatient appointments, prior to being seen in clinic. Questionnaires should be completed independently by the participant. If a participant requires assistance from a caregiver, this should be recorded on the form. The forms will then be sent to CTRU.

Where a participant/caregiver has expressed a preference to complete their questionnaires via REDCap online, the participant/caregiver will be sent a link to the questionnaire via text or email. They will also be sent reminders to prompt completion of the data, this includes reminders by their preferred method, either text message or email. Please note: online questionnaires can be completed on any device and do not have to be completed on a mobile phone. If participants/caregivers would prefer to complete questionnaires on a desktop computer, a prompt or reminder sent by email should be the preferred option for communication about questionnaire completion, please see Section 9.18 Trial assessments and data collection for further information.

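### Reminders for the end-of-radiotherapy questionnaires, sent 2 and 4 weeks after the link, come too late to prompt an answer during the last five fractions

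*Protocol*

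**What the plan says.** Section 9.5 of the protocol states that the final-week assessments "should be completed on any day the participant receives one of their 5 final radiotherapy treatments". These include the HRQoL questionnaires, WPAI and the Caregiver Needs Screen. Table 3 marks the same three rows with footnote 12: "To be completed on any day the participant will receive one of their 5 final RT treatments".

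Section 9.18 lists the time points at which non-responders are reminded as "during the final week of RT treatment and 1, 3, 6, 12, 24, 36, 48 and 60 months post-end of RT". One timing covers all of them: "Reminders will be sent 2 weeks and 4 weeks after the initial link to the questionnaire was sent". No shorter interval is given for the final week, and no date is given on which that link closes.

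The reminders are counted from an electronic link, so they concern people who chose REDCap. For those who chose paper, section 9.12 says that "questionnaires will be completed by the participant/caregiver on attendance at the scheduled outpatient appointments, prior to being seen in clinic".

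**The concern.** The final-week time point has a window of about one week, and the reminder interval is two weeks. A reminder exists to recover a missing form while the answer still describes the intended period. Here it can only recover a form that describes a later one.

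This matters because Table 3 shows no other post-baseline questionnaire during radiotherapy. If part of the electronic group answers one to four weeks after treatment, that time point mixes answers from two periods. The mixture depends on mode of completion, because paper forms are filled in at the clinic. The second reminder also reaches the participant or caregiver at about the time the 1-month questionnaire is due, so two requests for different nominal time points may be open together.

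**Working it through.** The protocol states no figure to reproduce; the check is one of dates.

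**Inputs**
- Fractions: "54 Gy(RBE) in 30 daily fractions for grade II tumours and 59.4 Gy(RBE) in 33 daily fractions for grade III tumours" (section 8.1), given on weekdays.
- Window: the days of the last five fractions (section 9.5; Table 3 footnote 12).
- Reminders: 14 and 28 days after the link (section 9.18).
- Assumption: the link is sent on one of the last five fraction days. The protocol does not give the link date.

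**Step 1: length of the window.** Five consecutive weekday fractions run Monday to Friday (5 calendar days) or cross one weekend (7 calendar days). The first of the five is therefore 4 or 6 days before the last fraction.

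**Step 2: reminders in an uninterrupted course.** Let *k* be the number of days from the link to the last fraction, with *k* between 0 and 6.
- First reminder: 14 − *k* days after the last fraction, so 14 − 6 = 8 to 14 − 0 = 14 days.
- Second reminder: 28 − *k* days, so 28 − 6 = 22 to 28 − 0 = 28 days.

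Listing 30- and 33-fraction courses for every starting weekday gives the same ranges.

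**Step 3: interruptions.** Missed weekdays were inserted before the last two fractions. The table gives days after the last fraction; a negative value is before it.

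| Missed weekdays | First reminder | Second reminder |
|---|---|---|
| 0 | 8 to 14 | 22 to 28 |
| 2 | 4 to 14 | 18 to 28 |
| 5 | 1 to 14 | 15 to 28 |
| 6 | 0 to 14 | 14 to 28 |
| 7 | −3 to 14 | 11 to 28 |

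The first reminder reaches the last fraction day only with six missed weekdays inside the final five fractions, and only if the link went out on the first of those five. Section 11.2 counts a course as adherent with no more than two treatment days of interruption.

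**Step 4: an earlier link.** For the first reminder to arrive by the last fraction, the link must go out at least 14 days before it. That is at least 14 − 6 = 8 days before the window opens.

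**Step 5: overlap with the 1-month questionnaire.** Taking one month as 28 to 31 days, the second reminder in an uninterrupted course comes 28 − 28 = 0 to 31 − 22 = 9 days before that questionnaire is due. Section 9.7 allows follow-up assessments "within +/- 4 weeks of the scheduled follow up timepoint", so the reminder falls inside the 1-month visit window.

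**The case against.** The strongest reply is that section 9.18 governs only when a prompt is sent. Section 13.1 describes the analysis section as an overview and defers detail to a separate SAP, which may well set analysis windows and deal with late forms. That stands: the absence of a late-form rule from the protocol is not a fault. It does not rescue the reminders, though. A SAP can exclude or relabel a late form, but it cannot obtain an answer that was not prompted in time.

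Other parts of the reply also stand:
- Section 9.5 says *should*, so a late form is not barred.
- The link date is not given. A link sent well before the window, or a long break near the end, could bring the first reminder into radiotherapy (steps 3 and 4).
- Participants attend on weekdays and are reviewed weekly, including in the final week, so staff can prompt them in person. This may keep the number of late forms low.
- The consequence is limited. WPAI and the Caregiver Needs Screen receive summary statistics only, HRQoL is secondary, and this is one of nine post-baseline time points.

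A reader might infer that late forms will be analysed as scores taken on treatment. The protocol does not say so; it is silent on them. Nor is this the only questionnaire during trial treatment. Section 10.1.2 counts adjuvant chemotherapy as trial treatment, and the 3- and 6-month questionnaires will usually fall within it. The supportable statement is that it is the only post-baseline one during radiotherapy.

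**Conclusion.** The reminder schedule does not fit the window of the final-week questionnaires. For electronic completers on an ordinary course, with the link sent during the last five fractions, the reminders come 8-14 and 22-28 days after the last fraction. Neither can prompt an in-window response, and the second coincides closely with the 1-month questionnaire. Forms returned after a reminder describe the period after radiotherapy and differ in timing from paper forms completed in clinic.

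A reader might go further and put a number on the bias in the end-of-radiotherapy mean or in the arm difference. That would need the share of forms returned only after a reminder, the size of the acute deficit and the speed of recovery. The protocol gives none of these. Quick recovery cannot be taken for granted either: Appendix B, Table B1 lists fatigue, headaches and nausea as expected up to 3 months after treatment. The size of any bias therefore remains unknown.

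The neurocognitive tests are not done in the final week, so the primary endpoint, its power and the interim decisions are untouched. Severity is minor.

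**What to change.** In section 9.18, give the final-week questionnaires their own schedule:
- Send the link on the first of the last five fraction days.
- Send reminders within the window, for example 2 and 4 days after the link. The last fraction comes 4 or 6 days after the first of the five, so both would arrive by the last fraction day of an uninterrupted course.
- Back this with a prompt at the final weekly review.
- Close the link before the 1-month questionnaire opens.

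Handling of any late forms that remain can be left to the SAP.

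The cost is a changed reminder setting in REDCap for one time point and a sentence or two in 9.18. Some forms that would have come in late become missing, but they would have been out of window. The change works only prospectively, because an answer not given during radiotherapy cannot be collected afterwards.

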#### 9.18.1 General eCRF completion guidance

Participating sites will record trial participant data via RDE onto eCRFs, using the MACRO database system, which will be managed by the CTRU. Access to the RDE system will be provided by the University of Leeds following the site being authorised to open to recruitment; guidance on RDE and completing eCRFs will be provided.

Participating sites will be expected to maintain a file of essential trial documentation in an ISF, which will be provided by the CTRU, and keep copies of all completed paper CRFs for the trial.

It is the responsibility of the site staff to ensure the ISF is properly maintained during the duration of the trial.

